8.5.3 SAFETY ANALYSES

Laboratory response variables will be descriptively summarized in accordance with time point and as changes from baseline including 95% confidence intervals. Laboratory values considered clinically significant will be presented in listings for participants in the safety population.

Measurements for vital signs as well as changes from baseline will be descriptively summarized by time point for participants in the safety population.

Serum pregnancy at Screening and urine pregnancy at each post baseline time point will be descriptively summarized for participants in the safety population.

The percentage of participants with abnormal medical history findings will be summarized by body system and preferred term for participants in the safety and mITT populations.

For statistical analysis purposes, prior medications are defined as those that were used and stopped before the start of the trial (prior to Day 0) and concomitant medications are defined as those used during the course of trial (on or after Day 0). Partial stop dates of prior and concomitant medications will be assumed to be the latest possible date consistent with the partial date. Data for all prior and concomitant medications will be summarized with percentages for participants in the safety and mITT populations.

8.5.4 DISPOSITION

Subject disposition will be summarized for all randomized participants and will include the number and percentage randomized, the number and percentage who received each planned dose and the number who completed each part of the trial. The number and percentage of participants who discontinued IP in each part of the trial will be summarized overall and by reason. The number in each analysis population will also be presented.

8.5.5 DEMOGRAPHIC AND OTHER BASELINE CHARACTERISTICS

[figure not shown]
Demographic and baseline characteristic data will be descriptively summarized for participants in the safety and mITT populations.

8.5.6 INTERIM ANALYSES

No formal interim analyses will be performed for this trial. However, safety and tolerability will be assessed by the DSMB as noted above for the participants in each Study Group.

A Sponsor unblinded review of the week 10 immunogenicity and safety data will be made during Part 1 of this study when all evaluable data observations are available in order to determine the optimal dose for the Part 2 of the study. The selection of the optimal dose for Part 2 will involve consideration of weighted ordered criteria described in [Figure 3](#) below.

Figure 3: Weighted Ordered Dose Selection Criteria

At a minimum, the optimal selected dose will have a 70% overall immune response and acceptable safety profile as determined by the DSMB and Inovio Medical Council. Other criteria listed in [Figure 3](#) will contribute to the selection of the right optimal dose if the overall immune responses and safety profiles are similar between the Study Groups in Part 1.

A group-level unblinded review of the immunogenicity and safety data will be made once week 12 visit data are complete for all participants in Part 2 whilst maintaining subject-level blinding. Long-term follow-up data will continue to be collected for all participants with remaining visits through to the final visit. These summaries and analyses will allow the Sponsor and collaborators to have results with respect to the immunogenicity and safety endpoints up to and including the Part 2 Week 12 visit on which to inform product development goals. No subject-level immunogenicity data will be produced and subject-level immunogenicity data will not be available in the clinical trial database until all other clinical trial data are finalized at the end of the trial. Thus, Part 2 of the trial will remain blinded to the Sponsor and collaborators with respect to subject treatment assignment.

In order to protect the blind, for the group-level unblinded review, no safety analysis will be provided if the total of subjects who experience the event of interest is greater than 0

and the count of these events relative to the total count of events produces a percentage less than 3% for a given analysis.

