All Part 1 participants will be followed for 48 weeks from the Day 0 dosing [i.e., Week 48 will be the planned End of Study (EOS) visit].

Part 2 – Expansion

In Part 2, approximately 350 participants will be evaluated across one (1) dose level and regimen as outlined in [Table 2](#) and [Table 3](#). The dose level and regimen will be identified based on the optimal dose selection from Part 1. Enrollment into Part 2 may begin following completion of the Week 10 optimal dose and regimen selection in Part 1 (i.e., prior to Week 48 completion in Part 1).

In Part 2A, participants will be randomized to receive the optimal dose of active (INO-4700) selected in Part 1 of this study or placebo (SSC-0001) ([Figure 1](#)). Approximately 300 participants will receive INO-4700 and 50 participants will receive placebo.

In Part 2B, the first 200 participants randomized to the Part 2A Active Study Group will receive a third dose of either INO-4700 or placebo at Week 48. Specifically, Study Group “Active – Booster” will receive INO-4700 at the first (Day 0), second (Week 4 or 8) and third (booster at Week 48) doses. Study Group “Active – Placebo” will receive INO-4700 at the first (Day 0) and second (Week 4 or 8) doses, and placebo at the third (Week 48) dose. Similarly, in Part 2B, the first 25 participants randomized to the Part 2A Placebo Study Group will receive a third dose of placebo at Week 48. Collectively, these first 225 participants will be followed for 68 weeks from the Day 0 dosing [i.e., Week 68 will be the planned End of Study (EOS) visit]. All remaining 125 participants in Part 2A (i.e., those receiving only 2 doses) will be followed for 48 weeks from the Day 0 dosing [i.e., Week 48 will be the planned End of Study (EOS) visit].

All participants and all clinical site staff will remain blinded to the subject treatment allocation (i.e., INO-4700 or placebo), with the exception of the site’s pharmacy personnel. Enrollment into Active and Placebo Study Groups will proceed in parallel. No enrollment pauses are planned.

Upon completion of the Week 12 visit and availability of immunological and safety data, group-level (INO-4700 or placebo) unblinded summaries of immunogenicity and safety will be produced. This Week 12 analysis will serve to inform product development goals. The Sponsor will continue to remain blinded to subject-level treatment allocation (i.e., INO-4700 or placebo) for the remainder of the trial.

DSMB for Parts 1 and 2

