8.5 DESCRIPTION OF STATISTICAL METHODS

8.5.1 PRIMARY SAFETY ANALYSES

The primary analyses for this trial are safety analyses of treatment emergent adverse events (TEAEs), administration site reactions and clinically significant changes in safety laboratory parameters from baseline.

TEAEs are defined for this trial as any AEs/AESIs/SAEs that occur on or after Day 0 following IP administration. All TEAEs will be summarized by frequency, percentage and associated 95% Clopper-Pearson confidence interval, and in Part 2, the difference in the percentage between those who received INO-4700 and their corresponding same regimen placebo together with associated 95% confidence interval. Related SAEs and related Grade 3 or higher AEs will also be analyzed as described above within and between associated placebo in part 1. The frequencies will also be presented separately by dose number and will be depicted by system order class and preferred term. Additional frequencies will be presented with respect to maximum severity and relationship to IP. Multiple occurrences of the same AE in a single subject will be counted only once following a worst-case approach with respect to severity and relationship to IP. All serious TEAEs will also be summarized as above. AE duration will be calculated as AE stop date – AE start date + 1 day. AEs and SAEs that are not TEAEs or serious TEAEs will be presented in listings.

All of these primary safety analyses will be conducted on the participants in the safety population.

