8.7 RANDOMIZATION AND BLINDING

Part 1 of this study will be randomized across Study Groups (A through I). Part 2 of this study will be randomized between the selected optimal Active dose from Part 1 and placebo groups. The study is Investigator-and-participant blinded except for the site pharmacy across all Study Groups for both parts of the study. The Sponsor will be blinded in Part 1 until Week 10 and blinded for the entire duration of Part 2 of the study.

For the Part 2 Week 12 analysis, group level unblinded summaries of immunogenicity and safety will be produced. The Sponsor will continue to remain blinded to subject-level treatment allocation for the remainder of the trial.

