3.12. Interim Analyses

No formal interim analyses are planned for this study. However, safety and tolerability will be assessed by the DSMB for the participants in each study group.

A Sponsor unblinded review of the Week 10 immunogenicity and safety data will be made during Part 1, when all evaluable data observations are available for determination of the optimal dose for Part 2.

Additionally, upon completion of the Week 12 visit and availability of immunological data, group-level (INO-4700 or placebo) unblinded summaries of immunogenicity and safety will be produced.

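### The Part 2 blind-protection rule divides events by events, so small safety tables can print single-case rows by arm while large ones withhold moderately frequent terms

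*Protocol*

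**What the plan says.** The rule is the last paragraph of Protocol v2.0 section 8.5.6. Its purpose and scope are explicit: "In order to protect the blind, for the group-level unblinded review, no safety analysis will be provided" when two conditions hold. The first counts participants: "if the total of subjects who experience the event of interest is greater than 0". The second is a ratio of events, taken for a given analysis: "the count of these events relative to the total count of events produces a percentage less than 3" per cent. No minimum number of participants is set and no participant denominator appears. The v2.0 summary of changes describes the same ratio.

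The review compares INO-4700 with placebo. Protocol 3.0 gives the Part 2 sizes: "Approximately 300 participants will receive INO-4700 and 50 participants will receive placebo". Protocol 8.7 says what must be preserved: "The Sponsor will continue to remain blinded to subject-level treatment allocation" to the end of the trial.

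The SAP plans the same review in section 3.12, where "group-level (INO-4700 or placebo) unblinded summaries of immunogenicity and safety will be produced". The supplied SAP text contains no suppression rule.

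**The concern.** A row in a two-arm table reveals allocation when few participants are in it, and with certainty when there is only one. The rule does not measure that. It measures a term's share of all events in the analysis, so whether a lone case prints depends on how many unrelated events share the table.

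The Sponsor can link such a row to a person. Protocol 7.9 requires SAEs and AESIs to reach the Sponsor within 24 hours, and 7.10.1 makes the subject number a minimum item of the report. Under 12.1 the Sponsor's Medical Monitor also reviews safety data throughout, blinded. A single case under one column therefore supplies the one thing the Sponsor is meant not to know.

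In the other direction, the rule can remove terms with little disclosure risk from a review whose purpose is to guide development.

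**Working it through.** **Inputs.** Threshold 3%, events over events (Protocol 8.5.6). Allocation 300:50, total 350 (Protocol 3.0). Erythema 63.3% by the intradermal route, from preliminary data (Protocol 1.4). The documents do not give the number of events in any Part 2 table, so totals are assumed and shown as a range. The 3% is a chosen cut-off with no derivation, so there is no stated figure to reproduce.

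**Rule as written.** With c events of a term and T events in the analysis, a term is withheld if c > 0 and c/T < 0.03. This takes T as specific to each table and suppression as row by row.

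**Single-case rows.** 1/33 = 3.03%, printed. 1/34 = 2.94%, withheld. Every analysis with 33 or fewer events therefore prints its single-case rows.

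**Which tables are that small?** The documents do not list the tables in the Week 12 review, so this is inferred from the planned safety analyses.
- Serious TEAEs: Protocol 8.5.1 says "All serious TEAEs will also be summarized as above". At assumed SAE rates of 0.5% to 5%, one event each, 350 × 0.005 = 1.75 and 350 × 0.05 = 17.5, or about 2 to 18 events. All single-case rows would print.
- AESIs: plausibly small, although Appendix B counts COVID-19 as an AESI, which could push this table past 33 events.
- Related Grade 3 or higher events: also plausibly small. Protocol 8.5.1 names this analysis explicitly only for Part 1, but tabulation by severity and relationship is general.

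**Large tables.** Largest count withheld, by assumed total:

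| Total events T | Largest count withheld |
|---|---|
| 350 | 10 |
| 500 | 14 |
| 700 | 20 |
| 1000 | 29 |
| 2000 | 59 |

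**Disclosure risk.** Let k participants have the event, with no treatment effect. The chance that all k are in one arm is the product of (300 − i)/(350 − i) for i = 0 to k − 1, plus the same product with 50 in place of 300. For k = 2: (300·299 + 50·49)/(350·349) = 0.75.

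| k participants | Chance all in one arm |
|---|---|
| 1 | 1.00 |
| 2 | 0.75 |
| 3 | 0.63 |
| 5 | 0.46 |
| 10 | 0.21 |
| 20 | 0.04 |

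So a small table prints the rows that disclose with certainty, while a large table can withhold rows that seldom disclose.

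**Very common reactions.** 63.3% of 300 is about 190 participants. At one event each, that is 190/700 = 27% of a 700-event table and 190/2000 = 9.5% of a 2000-event table, both above 3%, so such terms print.

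**The case against.** **The denominator is not defined.** If total events means all TEAEs in the review whatever the table, a single SAE would be a tiny fraction and would be withheld, and the main disclosure route closes. This is a fair reading, although the qualifier limiting the ratio to a given analysis points to a table-specific total. The over-suppression remains under it. If the authors meant participants over participants, the wording is wrong. The text also leaves open whether a row or a whole analysis is withheld.

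**A reader might infer that the rule hides common reactions.** It does not: a reaction as frequent as erythema prints. What is lost is the moderately frequent term, and how frequent depends on a total the documents do not give.

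**A reader might infer that a withheld 20-event row could identify nobody.** Events are not people, since recurrent events may come from a few participants. Even 20 separate participants all fall in one arm about 4% of the time.

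**A reader might infer that programming to the SAP would print everything.** This cannot be confirmed. SAP 1.2.2 refers to a randomization plan in Appendix B that is not in the supplied text. The SAP undertakes in 1.1.2 to record departures from the protocol, and section 5 does not list this rule as dropped. What stands is that SAP 3.12 describes the review without it.

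**The consequence is small.** The Part 2 primary test is a single-arm exact binomial on laboratory response, and Protocol 8.5.6 keeps subject-level immunogenicity data out of the database until the end. Knowing a few SAE participants' arms could hardly bias it. Under 5.2.1 pharmacovigilance staff may already unblind related, unexpected events. With 6:1 allocation, a lone active-arm case moves a prior of 86% to certainty. All of this stands and limits the importance. It does not remove the point: Week 48 dosing and per-protocol exclusions come after Week 12, and the plan itself undertakes to keep the blind.

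**Conclusion.** The concern holds as a minor fault in the plan. Following the rule literally, with a table-specific denominator and row-level suppression, defeats its stated aim in any analysis with 33 or fewer events, most clearly the serious TEAE table. It also withholds terms of up to 10 to 59 events when totals run from 350 to 2000. The 33-event boundary follows from the 3% alone; the sizes in large tables rest on assumed totals. If the denominator was meant to be all TEAEs, only the over-suppression survives.

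The documents do not support inferring that any participant's allocation was disclosed. The protocol administrative memo on discontinuation records that Part 2 would not proceed, so the rule was never applied and no reported result is affected. The value of correcting it lies in not reusing the wording.

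**What to change.** Base the rule on participants. One way keeps the 3% cut but defines it as participants with the event, both arms combined, divided by all participants in the review. With 350 participants, 0.03 × 350 = 10.5, so the rule covers terms affecting 10 or fewer. A single case is 1/350 = 0.29% and is always covered, however many other events are in the table.

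- Show covered terms pooled across arms rather than withholding them, so the information is kept.
- Pool any SOC or total row from which a covered term could be recovered by subtraction.
- State that the rule applies per row.
- Carry identical text into SAP 3.12.

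A much lower cut, such as pooling only terms with fewer than three participants, would be weak: three cases all fall in one arm with probability 0.63 under 300:50 and no effect. Even with the proposed cut some risk remains. The smallest term shown by arm has 11 participants, and the same formula gives 0.18 that all are in one arm.

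The cost is rewording one paragraph and copying it to the SAP. Rare terms lose their arm labels in this one review. DSMB reviews and final analyses are unaffected.

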8.5.7 MULTIPLICITY

No adjustment for multiplicity will be made for this trial.

8.5.8 MISSING VALUES

Missing data will not be imputed or replaced, and calculations will be done on reported values.

8.5.9 EXPLORATORY ANALYSES

T and B post baseline cell number will be analyzed descriptively by Study Group using the mean or median and associated 95% confidence intervals.

In Part 2, treatment difference comparisons will include a comparison of two dose INO-4700 participants who are boosted with INO-4700 versus two dose INO-4700 participants who are boosted with placebo.

Exploratory ANCOVA and Logistic models may be fit that include baseline, confounder variables such as age, antibodies to other coronaviruses and gender to test the relationship between study group and different immune response variables. The relationship between antibodies to other coronaviruses and humoral immune responses will be explored using regression methods such as linear regression.

8.6 SAMPLE SIZE/POWER

No formal power analysis is applicable to Part 1 of this trial, as descriptive statistics will be used to summarize the data.

For each Study Group in Part 1 of the trial with 32 INO-4700 administered participants, the study provides 95% confidence that the true incidence of SAEs is <11% if no SAEs are observed in a study group. For all the Study Groups combined in Part 1 of the trial with 160 INO-4700 administered participants, the study provides 95% confidence that the true incidence of SAEs is <3% if no SAEs are observed in this study phase. For all Study Groups combined across Parts 1 & 2 of the trial with 460 INO-4700 administered participants, the study provides 95% confidence that the true incidence of SAEs is <1% if no SAEs are observed.

For Part 2 of this trial, an evaluable sample of 260 active subjects treated with INO-4700, which will be used for formal hypothesis testing, provides >90% power to detect an INO-4700 overall immunological response rate of 70% or higher should this overall response rate truly be 80%, using a one-sided type 1 error rate of 0.025.

8.7 RANDOMIZATION AND BLINDING

Part 1 of this study will be randomized across Study Groups (A through I). Part 2 of this study will be randomized between the selected optimal Active dose from Part 1 and placebo groups. The study is Investigator-and-participant blinded except for the site pharmacy across all Study Groups for both parts of the study. The Sponsor will be blinded in Part 1 until Week 10 and blinded for the entire duration of Part 2 of the study.

For the Part 2 Week 12 analysis, group level unblinded summaries of immunogenicity and safety will be produced. The Sponsor will continue to remain blinded to subject-level treatment allocation for the remainder of the trial.

9.0 ETHICS

9.1 INVESTIGATOR AND SPONSOR RESPONSIBILITIES

The Investigator and Sponsor are responsible for ensuring that the clinical trial is performed in accordance with the protocol, the principles of the Declaration of Helsinki, Good Clinical Practice (GCP) and applicable regulatory requirements.

9.2 INSTITUTIONAL REVIEW BOARD (IRB)/RESEARCH ETHICS BOARD (REB)/ETHICS COMMITTEE (EC)

The Investigator will commence the clinical trial after full approval of the protocol and adjunctive materials (e.g., ICF, advertising) has been obtained from the applicable IRB/REB/EC and a copy of IRB/REB/EC approval documentation has been received by the Sponsor.

Investigator responsibilities relevant to the IRB/REB/EC include the following:

- Submit progress reports to the IRB/REB/EC as required, and request re-review and approval of the clinical trial at least once a year during the conduct of the clinical trial
- Notify the Sponsor immediately of any suspected unexpected adverse drug or device events/effects
- Notify the IRB/REB/EC immediately if the Sponsor notifies the Investigator about any reportable safety events
- Obtain approval from the IRB/REB/EC for protocol amendments and for revisions to the consent form or participant recruitment advertisements, as required
- Submit reports on, and reviews of, the clinical trial and its progress to the IRB/REB/EC at intervals stipulated in their guidelines and in accordance with pertinent regulations and guidelines
- Maintain a file of clinical trial-related information (refer to clinical trial files) that includes all correspondence with the IRB/REB/EC
- Notify the IRB/REB/EC when the clinical trial is completed (i.e., after the last clinical trial visit of the final clinical trial subject)
- After clinical trial completion (within three [3] months is recommended), provide the IRB/REB/EC with a final report on the clinical trial

Institutional Biosafety Committee (IBC), if applicable

The Investigator will undertake the trial after full approval of the protocol and adjunctive materials (e.g., pharmacy manual) has been obtained from the applicable IBC and a copy of this approval has been received by the Sponsor.

Investigator responsibilities relevant to the IBC include the following:

- Notify the Sponsor, IBC and NIH OSP within 30 days of any:
 - Substantial problems or violation of the NIH Guidelines
 - Significant research related accidents or illnesses
- Notify the IBC to any changes to the research (dosage, procedure, etc.) or facility (new space, remodeling, etc.).

9.3 PROTECTION OF HUMAN PARTICIPANTS

9.3.1 COMPLIANCE WITH INFORMED CONSENT REGULATIONS

Written informed consent must be obtained from each subject, and/or from the subject's legally authorized representative, prior to the subject's enrollment in the clinical trial. The process for obtaining informed consent must be documented in the subject's medical record (also refer to [Section 6.2](#)).

9.3.2 COMPLIANCE WITH INSTITUTIONAL REVIEW BOARD (IRB)/RESEARCH ETHICS BOARD (REB)/ETHICS COMMITTEE (EC) REQUIREMENTS

This clinical trial is to be conducted in accordance with applicable IRB/REB/EC regulations. The Investigator must obtain approval from a properly constituted IRB/REB/EC prior to initiating the clinical trial and obtain re-approval or review at least annually. The Sponsor is to be notified immediately if the responsible IRB/REB/EC has been disqualified or if proceedings leading to disqualification have begun. Copies of all IRB/REB/EC correspondence with the Investigator should be provided to the Sponsor.

